11.4 Data Analyses Plans

The TiTE-CRM estimates for the probability of DLT will be reported with 95% Bayesian Credible intervals, once the 32nd evaluable patient has completed the DLT observation period. The MTD/RP2D will be determined at that time as the dose level with the highest probability of DLT not exceeding 35%.

We will record ORR as a yes/no outcome for each patient for the period of active study treatment and report the estimate and exact 95% binomial confidence intervals. We will estimate PFS and OS using the product-limit method of Kaplan and Meier. Follow-up time will be defined as time from date of first study treatment until the date of radiological or clinical progression (leading to withdrawal from the study), or death from any cause, whichever comes first for PFS and for only death from any cause for OS. For patients without events, we will censor the follow-up time at the date of last disease evaluation at the time of analysis. We will report estimates for the median and 75th percentiles with 95% confidence intervals. We will summarize additional safety data (e.g., laboratory safety parameters, vital signs, concomitant medications and new physical examination findings) descriptively by reporting counts and percentages, with exact binomial confidence intervals where appropriate. ORR will be determined as per the RECISTv1.1 guidelines. We will report adverse events per the NCI CTCAE v5.0.

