2.4 Endpoints Assessment

- 2.4.1 Primary Endpoint Assessment: Determine the maximum tolerated dose/recommended phase 2 dose by assessment of dose-limiting toxicities (DLTs).
- 2.4.2 Secondary Endpoint Assessment: The progression-free survival (PFS) will be defined as time from date of treatment to date of radiological or clinical progression (leading to withdrawal from the study), or death from any cause, whichever comes first. The time to progression (TTP) will be defined as time from date of treatment to date of radiological or clinical progression (leading to withdrawal from the study). Follow-up time will be censored at the date of last disease evaluation. Overall survival (OS) will be defined from the date of treatment to either date of death or censoring. Adverse events and reportable serious events are defined by the study protocol (NCI Common Toxicity Criteria for Adverse Events (CTCAE) v5.0).

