5.7 Duration of Follow-Up

After treatment discontinuation, follow-up for survival and initiation of any other anti-cancer therapies will be documented every 3 months (+/- 1 week) via telephone or office visit documentation for up to 2 years from treatment discontinuation or until death, whichever comes first, or 3 years after first date of treatment initiation for those that remain on treatment. Patients removed from treatment for unacceptable adverse events will also be followed more closely until resolution or stabilization of the adverse event.

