 9. Patients will be followed every 3 months via telephone or office visit documentation for up to 2 years from treatment discontinuation or until death, whichever comes first, or 3 years after first date of treatment initiation for those that remain on treatment.
 10. Check AFP every 8 +/- 1 weeks. May be delayed if drug is not administered within the window.
 11. Urine protein/creatinine ratio
 12. Pharmacokinetic blood draws (pre-dose) prior to Cycle 1 Day 15, Cycle 2 Day 1, Cycle 2 Day 15 and Cycle 3 Day 1. See lab manual for details.

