7.0 MEASUREMENT OF EFFECT

7.1 Antitumor Effect- Solid Tumors

Objective response assessment will be determined by review of CT or MR scans of the chest, abdomen and pelvis using RECIST v1.1 every 8 weeks +/- 1 week while patients are on treatment (Eisenhauer, Therasse et al. 2009) .

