7.1.4.3 Evaluation of Best Overall Response

The best overall response is the best response recorded from the start of the treatment until disease progression/recurrence (taking as reference for progressive disease the smallest measurements recorded since the treatment started). The patient's best response assignment will depend on the achievement of both measurement and confirmation criteria.

Table 6. Response Evaluation as per RECISTv1.1				
Target Lesions	Non-Target Lesions	New Lesions	Overall Response per RECISTv1.1	Confirmed Response for this Category Requires:
CR	CR	No	CR	>4 wks. confirmation
CR	CR Non-CR/PD	No	PR	≥4 wks. confirmation
PR	CR Non-CR/PD	No		
SD	CR Non-CR/PD	No	SD	Documented at least once ≥4 wks. from baseline
PD	Any	Any	PD	
Any	PD*	Any		
Any	Any	Yes		

* Only in exceptional circumstances, unequivocal progression in non-target lesions may be accepted as disease progression.
 
Note: Patients with a global deterioration of health status requiring discontinuation of treatment without objective evidence of disease progression at that time should be reported as “symptomatic deterioration”. Every effort should be made to document the objective progression even after discontinuation of treatment.
				

NA=not applicable

Note: If subjects respond to treatment and are able to have their disease resected, the patient's response will be assessed prior to the surgery.

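### Section 11.4 censors OS, like PFS, at the last disease evaluation, which discards survivors' known follow-up and biases the Kaplan-Meier OS estimates downward

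*Combined protocol and SAP*

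**What the plan says.** Section 11.4 treats the two endpoints as a pair: "We will estimate PFS and OS using the product-limit method of Kaplan and Meier". The next sentence defines follow-up time for both, ending at progression or death for PFS and at death alone for OS. One censoring rule follows, not limited to either endpoint: "For patients without events, we will censor the follow-up time at the date of last disease evaluation at the time of analysis". The plan then reports the median and 75th percentile with 95% confidence intervals.

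Section 2.4.2 does not supply a different OS rule. After the PFS and TTP definitions it says "Follow-up time will be censored at the date of last disease evaluation". It then says "Overall survival (OS) will be defined from the date of treatment to either date of death or censoring", with no date for the censoring.

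The phrase disease evaluation is not defined. Section 7.1 schedules response assessment "using RECIST v1.1 every 8 weeks +/- 1 week while patients are on treatment", and the Section 6.2 calendar shows no scan at the end-of-treatment visit or in follow-up. Survival data continue well past that point. Section 5.7 says "follow-up for survival and initiation of any other anti-cancer therapies will be documented every 3 months", and footnote 9 of the calendar says "Patients will be followed every 3 months via telephone or office visit documentation for up to 2 years from treatment discontinuation".

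**The concern.** Last disease evaluation is a sensible censoring date for PFS, because progression status is unknown after it. It is the wrong date for OS, because vital status is known for longer.

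Under the written rule, two patients reached at the same survival contact are handled differently. If one has died, the death enters at its true date. If the other is alive, the months since the last scan are removed. Censoring time then depends on the outcome, which violates the non-informative censoring that Kaplan-Meier requires.

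OS is a named secondary endpoint in Section 2.2, so its reported median and 75th percentile would be biased. The loss falls mainly in the tail. OS carries no hypothesis or threshold, and dose selection does not use it.

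**Working it through.** **Plan's own figure.** None. The documents state no OS assumption, event count, precision target or OS analysis date, so the check covers direction first and then size under stated assumptions.

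**Direction.** The Kaplan-Meier estimate is S(t) = ∏ (1 − dᵢ/nᵢ) over death times up to t. Both rules use the same deaths dᵢ at the same times. Under the stated rule survivors are censored no later, and usually earlier, so each nᵢ is the same or smaller. Each factor is then the same or smaller, and the stated-rule curve can never lie above the curve censored at last known alive.

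**Inputs from the documents.** n = 32 (Section 11.2); scans every 8 weeks on treatment (Section 7.1); treatment for at most 24 months (Section 5.1.1); survival follow-up for up to 24 months after treatment (Section 5.7); study duration 3 years (Study Schema). The OS range runs from 3.8 months, the Child-Pugh B first-line sorafenib figure in Section 1.2, to 8.0 and 10.2 months, the two arms of the Child-Pugh A cabozantinib trial in Section 1.1. The latter two serve as an upper range only.

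**Assumptions not in the documents.** Exponential OS; uniform accrual over 24 months; cut-off at month 36 or 48; no tumour evaluations after treatment; 75th percentile read as the time by which 75% have died, S(t) = 0.25. Time on treatment is bracketed. The low end of each range makes it independent of survival with median 2 months; the high end makes it a Beta(2,2) fraction of survival.

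**Share alive at month 36.** Follow-up is uniform on 12 to 36 months, so with λ = ln 2 / median the share alive is [exp(−12λ) − exp(−36λ)] / (24λ):

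- median 3.8: (0.112 − 0.001)/4.38 = 2.5%
- median 6: (0.250 − 0.016)/2.77 = 8%
- median 8: (0.354 − 0.044)/2.08 = 15%
- median 10.2: (0.442 − 0.087)/1.63 = 22%

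Only these patients are handled differently by the two rules. At a true median of 8, the stated rule discards 38% to 90% of their known-alive time.

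**Simulation, cut-off month 36** (10,000 trials per setting; medians across trials, in months):

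| True median OS | Median, stated rule | Median, full survival follow-up | 75th percentile, stated rule | 75th percentile, full survival follow-up |
|---|---|---|---|---|
| 3.8 | 3.6 | 3.6 | 7.1–7.2 | 7.2 |
| 6 | 5.4–5.8 | 5.8 | 10.0–11.2 | 11.4 |
| 8 | 6.6–7.6 | 7.6 | 11.7–14.3 | 15.4 |
| 10.2 | 7.6–9.6 | 9.7 | 12.9–17.3 | 20.1 |

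The comparison is rule against rule; with n = 32 even the correctly censored median falls slightly below the true value. In relative terms, at true median 8 the worst case is 6.6/7.6 − 1 = −13% at the median and 11.7/15.4 − 1 = −24% at the 75th percentile; the mildest is no change and 14.3/15.4 − 1 = −7%.

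**Cut-off month 48.** True 8: median 7.1–7.6 against 7.6, 75th percentile 13.0–15.1 against 15.2. True 10.2: 8.3–9.8 against 9.8, and 14.6–18.8 against 19.4.

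**Second model.** An illness-death simulation (200,000 patients per setting) let scans stop at detected progression and censored survivors at the last scan or the last contact. Results for 24-month accrual and a month-36 cut:

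- OS 10, progression 4 months: median 9.37 against 9.98 (−6%), 75th percentile 14.63 against 16.53 (−11%)
- OS 10, progression 2 months: 8.27 against 10.01 (−17%), and 13.43 against 18.54 (−28%)
- OS 6, progression 2 months: 5.82 against 5.96 (−2%), and 9.78 against 10.37 (−6%)
- OS 3.8: no material difference

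With a cut at month 25, OS 10 and progression 2 months, the losses reach −25% and −35%. In 3,000 trials of 32 patients per setting, the stated rule never gave the higher quantile.

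**The case against.** The strongest reply is that Section 11.4 is a compressed sentence written with PFS in mind. Section 2.4.2 places the last-evaluation date after PFS and TTP and defines OS separately, and a 3-monthly survival follow-up makes little sense if survivors' data go unused. That may well be the intent. But no other OS rule is written down, so an analyst who uses last known alive departs from the plan after data are in hand. Reading disease evaluation to include telephone contacts would repair OS but damage PFS, by crediting progression-free time without a tumour assessment.

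The size argument has more force. The trial enrols Child-Pugh B7 and B8, and at the only Child-Pugh B median cited, 3.8 months, the effect vanishes. The larger losses need Child-Pugh A survival, and the low ends assume 2 months on treatment when the cited TTP medians are 4.2 and 3.8 months. Section 7.1.4.3 also says "Every effort should be made to document the objective progression even after discontinuation of treatment", and any such evaluations would shrink the bias. Sampling error is far larger: at true median 6, the correctly censored median spans about 3.3 to 9 months across 95% of trials, against a shift of 0 to 0.4 month. All of this stands. It limits the importance of the point, but bias in a known direction is not excused by wide intervals. The 3.8-month figure also comes from a first-line series that included B9 patients, and the OS analysis date is unstated.

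Finally, the ordering depends on what 75th percentile means. If it means the time at which 75% are still alive, the loss is smaller than at the median: 2.9–3.1 against 3.1 months at true 8, and 3.6–4.0 against 4.0 at true 10.2. The direction and the fix do not change.

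**Conclusion.** The concern holds. As written, the OS censoring rule is wrong, and its bias can only be downward. Size depends on how many patients are alive at analysis and how long before that their scans stopped. It ranges from nil at a 3.8-month median with a mature cut-off to, at month 36 with a true median of 10.2 months, −22% at the median (7.6 against 9.7) and −36% at the 75th percentile (12.9 against 20.1). An earlier analysis would enlarge it.

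The greater loss at the 75th percentile is a simulation result, seen in every setting with a visible bias, under the usual reading of that percentile. The sizes rest on assumed survival, accrual, treatment time and cut-off; the direction does not. This should be fixed before OS is analysed. It does not touch the primary endpoint.

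**What to change.** Split the rule in Sections 11.4 and 2.4.2, for example:

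> PFS and TTP: censor at the date of last disease evaluation. OS: censor at the date last known alive (visit, telephone contact or record), or at the data cut-off if earlier.

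State in 11.4 when OS will be analysed. It would also help to define disease evaluation as a tumour assessment and to say which tail the 75th percentile refers to.

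The cost is one sentence in two places. Section 5.7 and the calendar already collect the contact dates. A small shortfall can remain because contacts are 3 months apart: in the second model (OS 10, progression 4 months, month-36 cut) the corrected 75th percentile was 16.53 against a true 16.84, compared with 14.63 under the stated rule.

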12.0 ADMINISTRATIVE PROCEDURES

12.1 Ethics and Good Clinical Practice

This study must be carried out in compliance with the protocol and be consistent with Good Clinical Practice (GCP), as defined by the International Conference on Harmonization (ICH), WHO and any local directives.

The protocol, any amendments, and the subject informed consent will receive Institutional Review Board/Independent Ethics Committee (IRB/IEC) approval/favorable opinion before initiation of the study.

12.2 Data Management

All information will be recorded locally and entered into Case Report Forms (CRFs) on the web-based electronic data capture (EDC) system of the University of Michigan. Online access will be provided to each site by the Coordinating Center.

CRFs will be reviewed and source verified by the multi-site project manager (MSPM) during annual monitoring visits and prior to and between visits. Discrepant, unusual and incomplete data will be queried by the MSPM. The investigator or study coordinator will be responsible for providing resolutions to the data queries, as appropriate. The investigator must ensure that all data queries are dealt with promptly.

The data submission schedule is as follows:

- At the time of enrollment
 - Subject entry into the EDC
- Subject Status
- Demographics
- During study participation
 - All data should be entered online within 10 business days of data acquisition. *[Information on dose limiting toxicity events must be entered within one business day.]* Information on Serious Adverse Events must be entered within the reporting timeframe specified in Section 8.4 of the protocol.

All study information should be recorded in an appropriate source document (e.g. clinic chart).

12.3 Record Retention

The Investigators must retain all study records and source documents for the maximum period required by applicable regulations and guidelines, or institution procedures, whichever is longer.

13.0 DATA AND SAFETY MONITORING

This study will be monitored in accordance with the NCI approved University of Michigan Rogel Cancer Center Data and Safety Monitoring Plan, with oversight by the Rogel Cancer Center Data and Safety Monitoring Committee (DSMC).

The Sponsor-Investigator (S-I)/Study Principal Investigator will provide ongoing monitoring of data and patient safety in this trial and conduct regular data review with participating sites.

The Sponsor-Investigator (S-I)/Study Principal Investigator and/or the Project Manager/Delegate will review data and patient safety issues with participating sites in a **monthly** meeting. Depending on the protocol activity, the meeting cadence may be more frequent. This data review meeting may be achieved via a teleconference or another similar mechanism to discuss matters related to:

- Enrollment rate relative to expectations, characteristics of participants
- Safety of study participants (SAE reporting, unanticipated problems)
- Adherence to protocol (protocol deviations)
- Completeness, validity and integrity of study data
- Retention of study participants

Participating sites are required to ensure all pertinent data for the review period are available in the database at the time of the discussion.

Participating sites unable to participate in the data review meeting are required to provide written confirmation that their site has reviewed the relevant data and patient safety issues for the review period and their site's data are in alignment with the data reported in the database. Written confirmation is to be provided to the Project Manager/Delegate within the timeline requested to retain compliance with monitoring timelines.

Documentation of the teleconference or alternate mechanism utilized to review items above is to be retained in the Trial Master File.

The Project Manager/Delegate is responsible for collating the data from all participating sites and completing the Protocol Specific Data and Safety Monitoring Report (DSMR) form to document the data review meeting discussion.

The DSMR will be signed by the Sponsor-Investigator (S-I)/Study Principal Investigator or designated Co-Investigator and submitted to the DSMC on a **monthly** basis for independent review.

14.0 QUALITY ASSURANCE AND AUDITS

The Data and Safety Monitoring Committee can request a 'for cause' quality assurance audit of the trial if the committee identifies a need for a more rigorous evaluation of study-related issues.

A regulatory authority (e.g. FDA) may also wish to conduct an inspection of the study, during its conduct or even after its completion. If an inspection has been requested by a regulatory authority, the site investigator must immediately inform the Coordinating Center that such a request has been made.

15.0 CLINICAL MONITORING PROCEDURES

Clinical studies coordinated by The University of Michigan Rogel Cancer Center must be conducted in accordance with the ethical principles that are consistent with Good Clinical Practices (GCP) and in compliance with other applicable regulatory requirements.

This study will be monitored by a representative of the Coordinating Center of the Rogel Cancer Center. Monitoring visits will be made during the conduct of the study and at study close-out.

Prior to subject recruitment, a participating site will undergo site initiation meeting to be conducted by the Coordinating Center. This will be done as an actual site visit; teleconference, videoconference, or web-based meeting after the site has been given access to the study database and assembled a study reference binder. The site's principal investigator and his study staff should make every effort in attending the site initiation meeting. Study-related questions or issues identified during the site initiation meeting will be followed-up by the appropriate Rogel Cancer Center personnel until they have been answered and resolved.

Monitoring of this study will include both 'Centralized Monitoring', the review of source documents at the Coordinating Center and 'On-site Monitoring', an actual site visit. The first 'Centralized' visit should occur after the first subject enrolled completes [first treatment cycle/course]. The study site will send the de-identified source documents to the Coordinating Center for monitoring. 'Centralized' monitoring may be requested by the Coordinating Center if an amendment requires changes to the protocol procedures. The site will send in pertinent de-identified source documents, as defined by the Coordinating Center for monitoring.

The first annual 'On-site' monitoring visit should occur after the first five study participants are enrolled or twelve months after a study opens, whichever occurs first. The annual visit may be conducted as a 'Centralized' visit if less than three subjects have enrolled at the study site. The type of visit is at the discretion of the Coordinating Center. At a minimum, a routine monitoring visit will be done at least once a year, or once during the course of the study if the study duration is less than 12 months. The purpose of these visits is to verify:

- Adherence to the protocol
- Completeness and accuracy of study data and samples collected
- Proper storage, dispensing and inventory of study medication
- Compliance with regulations

During a monitoring visit to a site, access to relevant hospital and clinical records must be given by the site investigator to the Coordinating Center representative conducting the monitoring visit to verify consistency of data collected on the CRFs with the original source data. While most patient cases will be selected from patients accrued since the previous monitoring visit, any patient case has the potential for review. At least one or more unannounced cases will be reviewed, if the total accruals warrant selection of unannounced cases.

The Coordinating Center expects the relevant investigational staff to be available to facilitate the conduct of the visit, that source documents are available at the time of the visit, and that a suitable environment will be provided for review of study-related documents. Any issues identified during these visits will be communicated to the site and are expected to be resolved by the site in a timely manner. For review of study-related documents at the Coordinating Center, the site will be required to ship or fax documents to be reviewed.

Participating site will also undergo a site close-out upon completion, termination or cancellation of a study to ensure fulfillment of study obligations during the conduct of the study, and that the site Investigator is aware of his/her ongoing responsibilities. In general, a site close-out is conducted during a site visit; however, site close-out can occur without a site visit.

17.0 APPENDICES

Appendix I	ECOG Performance Status
Appendix II	Child-Pugh Status
Appendix III	List of Strong Inhibitors and Inducers of CYP3A4
Appendix IV	Investigator's Statement

Appendix I ECOG Performance Status

	Description
0	Fully active, able to carry on all pre-disease performance without restriction
1	Restricted in physically strenuous activity but ambulatory and able to carry out work of a light or sedentary nature e.g. light house work, office work.
2	Ambulatory and capable of all self-care but unable to carry out any work activities. Up and about more than 50% of waking hours.
3	Capable of only limited self-care, confined to bed or chair more than 50% of waking hours.
4	Completely disabled. Cannot carry on any self-care. Totally confined to bed or chair.

Source: Eastern Cooperative Oncology Group

